8.1 Definition

Unexpected events that have not been defined as endpoints (section 7) or expected complications of the PCI procedure (listed in section 7.4) should be reported as either a serious adverse event (SAE) or non-serious adverse event (NSAE) depending on their severity.

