8.2 Unexpected Serious Adverse Events

SAEs should be reported to the Clinical Trials Unit (CTU) within 7 days of the site becoming aware of the event. The report should include an assessment of causality by the Principal Investigator at each site (see section 5.4.2). The Chief Investigator will be responsible for the prompt notification of findings that could adversely affect the health of patients or impact on the conduct of the trial.

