8.3 Unexpected Non-Serious Adverse Events

Unexpected NSAEs should be evaluated by the Principal Investigator. This should include an assessment of intensity (see section 8.4.1) and causality (see section 8.4.2) and reports made within 14 days of the site becoming aware of the event. The CTU will keep detailed records of all unexpected adverse events reported. Reports will be reviewed by the Chief Investigator to consider intensity, causality and expectedness.

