8.4.1 Assessment of Intensity

Mild: The patient is aware of the event or symptom, but the event or symptom is easily tolerated.

Moderate: The patient experiences sufficient discomfort to interfere with or reduce his or her usual level of activity.

Severe: Significant impairment of functioning; the patient is unable to carry out usual activities and/or the patient's life is at risk from the event.

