8.5 Notification

The Sponsor, the Research Ethics Committee (REC) and the Data Monitoring Committee (DMC) will be notified by the CTU when reported SAEs have been classified by the Chief Investigator as **both** unexpected and given a causality classification of either Probable or Possible.

9. Ethical Considerations

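### Protocol 8.1 separates SAEs from NSAEs by severity and nothing defines serious by outcome, so a related unexpected event that led to or prolonged admission can fall outside the 8.5 notification rule

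*Protocol*

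**What the plan says.** Section 8.1 first removes endpoint events and the expected complications listed in 7.4. The remaining unexpected events "should be reported as either a serious adverse event (SAE) or non-serious adverse event (NSAE) depending on their severity".

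The class then determines what happens next:

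- **8.2, serious:** "SAEs should be reported to the Clinical Trials Unit (CTU) within 7 days of the site becoming aware of the event", with a causality assessment by the site's Principal Investigator.
- **8.3, non-serious:** the Principal Investigator evaluates the event. "This should include an assessment of intensity (see section 8.4.1) and causality (see section 8.4.2) and reports made within 14 days" of the site's awareness. The Chief Investigator reviews reports for intensity, causality and expectedness.
- **8.4:** all unexpected events, serious or not, go to the CTU.
- **8.5:** the CTU notifies the sponsor, the REC and the DMC "when reported SAEs have been classified by the Chief Investigator as" both unexpected and either Probable or Possible in causality.

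The only graded scale is in 8.4.1, headed intensity. Its middle grade reads "Moderate: The patient experiences sufficient discomfort to interfere with or reduce his or her usual level of activity". Its top grade covers significant impairment of functioning, where "the patient is unable to carry out usual activities and/or the patient's life is at risk from the event". Section 19.6 repeats the two deadlines and refers back to section 8. The abbreviation list expands SAE but does not define it.

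**The concern.** Severity describes how intense an event is. Seriousness describes its outcome: death, threat to life, admission or prolonged admission, lasting disability. The two often diverge. An event can prolong a hospital stay while causing little discomfort, and an intense symptom can pass without consequence. Section 8.1 uses the first concept to do the work of the second.

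What is at stake is safety oversight of a device strategy, not the primary analysis. Harms that 7.4 does not list reach the CTU as adverse event reports only through section 8, and only those classed as SAEs can trigger notification under 8.5. If admission does not count in the classification, a related and unexpected event with a serious outcome may not be notified.

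**Working it through.** No power, alpha or event count enters this point, so there is nothing numerical to reproduce. The check follows an event through the text.

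**Step 1: is there another definition of serious?** Sections 7.4, 8.1 to 8.5 and 19.6 and the abbreviation list contain no outcome-based criteria for an SAE. Section 9.2 commits to GCP in general terms and states no criteria.

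**Step 2: can severity in 8.1 stand in for one?** There are two readings, and they exclude each other.

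- *Severity means the 8.4.1 grade.* This is an inference, since 8.1 does not cite that scale, but no other scale is given. The grades turn on discomfort, function and risk to life. None mentions admission. Nor does 8.1 say which grade makes an event serious. An event that prolongs admission and is graded moderate can be an NSAE.
- *Severity is an ordinary word left to the site.* Admission is again not a stated criterion, and a site that judges the event not severe files an NSAE.

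The conclusion needs only one of these, and it follows under either.

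**Step 3: what changes with the class?** Take an unexpected event outside 7.4 that led to or prolonged admission and is judged Probably or Possibly related.

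| | Filed as SAE | Filed as NSAE |
|---|---|---|
| Report to CTU | within 7 days (8.2, 19.6) | within 14 days (8.3, 19.6) |
| CTU and Chief Investigator receive it | yes | yes |
| Stated central check of seriousness | none | none (8.3 covers intensity, causality, expectedness) |
| Sponsor, REC and DMC notified under 8.5 | yes | no route |

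The deadline moves by 14 − 7 = 7 days, and the 8.5 route is lost.

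**Step 4: does any event fall in the gap?** Most expected harms do not. Section 7.4 covers disabling stroke, MI, heart failure and arrhythmia admissions, BARC 3 to 5 bleeding, vascular complications, access-related injury, procedural complications and kidney injury. Under 19.6 these go in the eCRF without an SAE form. Two examples remain:

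- *Non-disabling stroke.* Section 7.4 requires a modified Rankin Scale of at least 3 at discharge, and 10.1 confirms that the component is disabling stroke. An ischaemic stroke below that threshold does not meet the definition. Intracranial haemorrhage would be caught as BARC 3c bleeding.
- *Haemolysis.* Section 2.2 reports it among the safety outcomes recommended by NICE, and 7.4 does not list it. Haemolysis that prolongs admission in a patient with few symptoms could be judged not severe.

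**The case against.** The strongest defence is that this is a slip of one word. The trial commits to GCP, trained site staff know what serious means, and the SAE and NSAE forms, which are not shown, may carry the criteria. A site might also reason that a patient in hospital cannot carry out usual activities and so grade the event severe. All of this may limit the effect in practice. None of it changes the rule that 8.1 states, and the general GCP commitment supplies no criteria to set against it.

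It is also fair to say that the affected set is narrow, for the reasons in the last step of the working, and that 8.5 would not notify an SAE judged unrelated either.

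Three stronger readings are tempting, and the protocol does not support them.

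- *Such events never reach the sponsor, REC or DMC.* All unexpected events go to the CTU, and the Chief Investigator reviews the reports. Section 8.2 gives the Chief Investigator a general duty to notify findings that could harm patients, although it names no recipients and sits under SAEs. The DMC charter is separate and not shown, so the DMC may see NSAEs by another path. What is missing is the route in 8.5.
- *Section 8.3 contradicts 8.1, so even a life-threatening event can be an NSAE.* Grading intensity among NSAEs does not say that an NSAE may take the top grade. It can equally suggest that intensity is meant to be separate from the class. This reading also needs severity in 8.1 not to mean the 8.4.1 grade, whereas the moderate-grade path needs that it does. Both cannot be asserted together.
- *SAE counts are unreliable and past reports are misclassified.* The protocol contains no evidence on how sites have classified events.

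**Conclusion.** The point holds as a wrong stated rule with a limited reach. Section 8.1 classifies by severity, no section defines serious by outcome, and the class controls both the deadline and the 8.5 notification. As written, an unexpected event outside 7.4 that led to or prolonged admission can be an NSAE if it is judged not severe. Its report is then due up to 7 days later. If it is also judged Probably or Possibly related, it has no route to the sponsor, REC and DMC under 8.5, and the central review has no stated step that would correct the class.

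The number of such events cannot be computed from the protocol. The conclusion assumes that sites apply 8.1 as written and that no form or charter outside the protocol supplies the missing criteria. It does not touch randomisation, power or the win ratio analysis. It should be corrected because safety oversight depends on it and the correction is cheap.

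**What to change.** 1. In 8.1, replace classification by severity with outcome-based seriousness: the event results in death, is life-threatening, requires or prolongs hospitalisation, causes persistent or significant disability, or is otherwise medically important.
2. Keep the 8.4.1 intensity grade as a separate descriptor, and ask for it in both 8.2 and 8.3.
3. Add seriousness to the items that the Chief Investigator reviews in 8.3, so that a wrongly filed NSAE can be reclassified and enter the 8.5 rule.
4. Check the NSAE reports already held once against the new definition. Section 8.3 has the CTU keep detailed records of all unexpected events, so this is feasible. It is a precaution and does not imply that errors have occurred.

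The cost is protocol wording and a one-off review of existing NSAE forms. No change to the design, sample size or analysis is needed.

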8.2 Unexpected Serious Adverse Events

SAEs should be reported to the Clinical Trials Unit (CTU) within 7 days of the site becoming aware of the event. The report should include an assessment of causality by the Principal Investigator at each site (see section 5.4.2). The Chief Investigator will be responsible for the prompt notification of findings that could adversely affect the health of patients or impact on the conduct of the trial.

8.3 Unexpected Non-Serious Adverse Events

Unexpected NSAEs should be evaluated by the Principal Investigator. This should include an assessment of intensity (see section 8.4.1) and causality (see section 8.4.2) and reports made within 14 days of the site becoming aware of the event. The CTU will keep detailed records of all unexpected adverse events reported. Reports will be reviewed by the Chief Investigator to consider intensity, causality and expectedness.

8.4 Reporting Unexpected Adverse Events

Investigators will make their reports of all unexpected adverse events, whether serious or not, to the CTU at the London School of Hygiene & Tropical Medicine.

8.4.1 Assessment of Intensity

Mild: The patient is aware of the event or symptom, but the event or symptom is easily tolerated.

Moderate: The patient experiences sufficient discomfort to interfere with or reduce his or her usual level of activity.

Severe: Significant impairment of functioning; the patient is unable to carry out usual activities and/or the patient's life is at risk from the event.

8.4.2 Assessment of Causality

Probable: A causal relationship is clinically / biologically highly plausible and there is a plausible time sequence between onset of the adverse event and the trial intervention.

Possible: A causal relationship is clinically / biologically plausible and there is a plausible time sequence between onset of the adverse event and the trial intervention.

Unlikely: A causal relationship is improbable and another documented cause of the adverse event is most plausible.

Unrelated: A causal relationship can definitely be excluded and another documented cause of the adverse event is most plausible.

8.5 Notification

The Sponsor, the Research Ethics Committee (REC) and the Data Monitoring Committee (DMC) will be notified by the CTU when reported SAEs have been classified by the Chief Investigator as **both** unexpected and given a causality classification of either Probable or Possible.

9. Ethical Considerations

9.1 Consent

Only patients that give written consent will be included in the trial. If fully informed consent is not possible, the patient will not be recruited into the trial. The patient should be given sufficient time to consider the trial following which informed consent will be taken. Consent may be taken once all requirements for inclusion have been met.

Staff at site may telephone potential patients with information about the trial before scheduled hospital appointments. If a patient is interested, then the site can post them the information sheet to read prior to their appointment and follow this up with a further telephone call within a reasonable time frame.

Patients at Participant Identification Centres (PICs) who meet the required eligibility criteria may be given the Participant Information Sheet (a localised version from the associated recruiting trial site). The review of eligibility and initial approach to the patient must be made by a member of their direct care team. It is then dependent on the patient to contact the relevant trial site to undergo informed consent and any further study procedures.

A patient may decide to withdraw from the trial at any time without prejudice to their future care.

9.2 Declaration of Helsinki and Good Clinical Practice

The trial will conform to the spirit and the letter of the Declaration of Helsinki, and in accordance with Good Clinical Practice (GCP) Guidelines.

9.3 Ethical Committee Review

The National Research Ethics Service Committee London - Bloomsbury have reviewed and approved the trial (REC reference 21/LO/0287). Copies of the letters of approval are to be filed in the trial site files at each centre.

10. Statistical Considerations

10.1 Win Ratio

The analysis will be undertaken by use of the Win Ratio, an increasingly recognised approach to allow for the hierarchy of events as well incorporating repeat events such as myocardial infarctions or hospitalisations[12,13]. The Win Ratio is the ratio of “winners” on the intervention compared to “losers” thus a value above 1 indicated a benefit of the intervention. Confidence intervals can be calculated as well as p-values and the process extended for repeat component events.

The combined hierarchical endpoint is all-cause death, stroke, spontaneous myocardial infarction (MI), cardiovascular hospitalisation and peri-procedural MI. The outcome hierarchy is as follows:

- (1) All-cause death
- (2) Stroke (defined as disabling stroke thus not including transient ischaemic attacks)
- (3) Spontaneous MI
- (4) Cardiovascular hospitalisation
- (5) Peri-procedural MI

The Win Ratio will use an unmatched pairs approach with each individual in the intervention arm compared to each individual in the standard care arm, using the stepwise sequence below, to adjudicate a winner/loser or declare a tie. For each comparison the common follow-up is defined in which follow-up is censored at the duration of the shorter follow-up interval. For example, if one patient has been followed for 1 year and the second patient for 2 years then for that specific comparison events up to one year will be considered.

- Step 1: Compare all-cause mortality – if one has died, the survivor is the winner, if both have died, the patient who survives longer is the winner and if neither has died (or both die at the same interval from randomisation) proceed to step 2
- Step 2: Compare time to occurrence of disabling stroke, as above. If no winner, proceed to step 3.
- Step 3: Compare time to occurrence of spontaneous MI (as per Universal Definition) as above. If no winner, proceed to step 4.
- Step 4: Compare the number of cardiovascular hospitalisations (as defined in the trial protocol). The patient with the least number of hospitalisations occurring within the common follow-up period is the winner. If the same number of hospitalisations have occurred, the patient who survives longer before the first hospitalisation is the winner. If neither have had a cardiovascular hospitalisation in this period, proceed to step 5.
- Step 5: Compare periprocedural MI. If only one has had a periprocedural MI, the patient who does not have a MI is the winner. If both have had a periprocedural MI, the patient with the smaller infarct size, as measured by peak Troponin level (expressed as a multiple of the 99th centile, to allow comparison of different Troponin assays) is the winner, unless the difference in increase in troponin level between patients is $\leq 5x$ the URL, in which case a tied will be declared. If neither patient has had a periprocedural MI, the stepwise comparison is concluded and the result declared a tie.

This approach is designed to optimise the impact of individual components of a composite endpoint, by allocating greater weight to more important events, increasing the range of events considered and allowing capture of recurrent events. The requirement for a $\geq 5x$ URL difference in troponin level in determining wins based upon peri-procedural MI is designed to ensure a clinically meaningful

difference in all declared wins. When analyses of recurrent events has been applied to simulated data and major contemporary heart failure trials precision has been shown to improve when treatment discontinuation is low following the first event[14]. Since the intervention is high-risk PCI and not drug therapy crossover rates are expected to be negligible allowing a smaller sample size whilst maintaining power. In contrast, a traditional composite endpoint trial using time to first event analysis weights each event equally and only incorporates the first event hence many more serious outcomes, such as death, may not included and no account is taken of later events. The sample size using such an approach would require a larger treatment difference to be detected (as illustrated below) or require a prohibitively large and expensive trial and would not be able to complete recruitment in a reasonable timeframe.

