7.4 Endpoint Definitions

Disabling Stroke	Stroke is defined as an acute episode of focal or global neurological dysfunction caused by brain, spinal cord, or retinal vascular injury as a result of hemorrhage or infarction, resulting in persistent moderate disability (modified Rankin Scale ≥ 3) at the time of discharge from the acute hospital admission.
Acute Myocardial Infarction	
1. Spontaneous MI (>48 hours after PCI/CABG) Detection of a rise and/or fall of cardiac Troponin I or T, with at least one value higher than the 99th percentile upper reference limit (URL) AND symptoms consistent with ischaemia OR dynamic electrocardiogram (ECG) changes (including ≥ 1mm ST elevation or ST depression, new left bundle branch block (LBBB) or >3mm T-wave inversion) OR imaging evidence of new loss of viable myocardium or new regional wall motion abnormality in a pattern consistent with an ischaemic aetiology.
 
2. Peri-procedural MI (<48 hours after PCI/CABG) Following PCI: Detection of a rise in cardiac troponin I or T, with the threshold of significance determined by the pre-procedure baseline value.
 
Baseline \leqURL: At least one value higher than five times the URL
 
Baseline $>$ URL and stable or falling: At least one value higher than 5xURL above the baseline value or 20% above the baseline value, whichever is greater.
 
Baseline $>$ URL and rising: At least one value higher than 5xURL above the predicted value* or 20% above the predicted value, whichever is greater.
 
*the predicted value will be calculated via linear extrapolation of the trend from at least two troponin values taken within 48 hours before the procedure.
 
Following CABG: As for PCI, but with a threshold of 10xURL. In addition to classifying patients dichotomously as having suffered a periprocedural MI or not, baseline and peak troponin I or T values measured within 24 hours of a procedure will be recorded. This will provide a continuous measure for adjudication of ties in patients reaching the periprocedural myocardial infarction endpoint within the Win Ratio.
 
Absolute values of troponin, ECGs and supporting information will be collected for all patients who experience a periprocedural MI, so that sensitivity analyses based on alternative definitions can be explored.

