10.2.1 Sample size extension

Due to successful recruitment, the opportunity arose for the investigators to extend recruitment and increase the sample size to 300 participants. The decision to design and conduct CHIP-BCIS was largely influenced by the position taken by NICE in 2018, when it was felt that there was insufficient evidence to support routine use of this strategy in the NHS and that more research on its safety and efficacy was a priority. Whilst a 30% relative risk reduction would enable NICE to issue clear guidelines on the use of LV unloading in the UK, increasing the sample size would allow an even smaller treatment effect to be assessed and hence provide NICE (as well as other healthcare systems and international guideline committees) with more definitive evidence on which to base their recommendations.

A further advantage of extending the accrual period is that the follow-up period of the 250 patients first recruited to the trial would be extended by the duration of the additional recruitment period. In total, we estimate that the proposed changes would lead to an increase in total follow-up by approximately 140 patient-years, which would allow capture of more clinical events, hence increasing statistical power. Given that the additional events captured will be those occurring later following randomisation, this will also potentially lead to more pairwise comparisons in the primary (win ratio) analysis being determined by components higher-up the hierarchy than peri-procedural MI, thereby also increasing clinical impact.

The TSC initially considered an increase in sample size in July 2023, subject to satisfactory progress in recruitment over the following 6 months. Accordingly, the TSC reviewed recruitment rates again in February 2024 and recommended an increase in the sample size to 300. An application to the funder was made in March 2024 and approved in May 2024.

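### Step 5 of the primary Win Ratio picks the winner of a both-MI pair on peak troponin but judges the tie on the increase, so the two halves of the rule can conflict

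*Protocol*

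**What the plan says.** The rule is in Protocol section 10.1, Step 5. For a pair in which both patients have had a periprocedural MI, the winner is "the patient with the smaller infarct size, as measured by peak Troponin level", in multiples of the 99th centile. The exception is a tie, which applies "unless the difference in increase in troponin level between patients is" at most 5x the URL.

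The paragraph after Step 5 explains the margin as a requirement for at least a 5x "URL difference in troponin level in determining wins based upon peri-procedural MI". That sentence says neither peak nor increase. It also places a difference of exactly 5x on the winning side, whereas Step 5 places it on the tied side.

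Section 7.4 defines periprocedural MI relative to baseline when baseline is raised. For a stable or falling raised baseline the threshold is: "At least one value higher than 5xURL above the baseline value or 20% above the baseline value, whichever is greater". For a rising baseline it uses a predicted value extrapolated from "at least two troponin values taken within 48 hours before the procedure". The same section says that "baseline and peak troponin I or T values measured within 24 hours of a procedure will be recorded", and gives the purpose: "This will provide a continuous measure for adjudication of ties". It does not say whether peak or increase is the measure to compare.

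**The concern.** This is the operative rule for the last tier of the primary endpoint, and its two clauses rank patients on different scales. The scales agree when pre-procedure troponin is low. They can disagree when one patient starts high. The protocol expects such patients: section 7.4 has two separate rules for raised baselines, and section 11.1 lists inpatients with acute coronary syndrome or acute heart failure as a screening source.

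If the scales disagree, some wins are settled by troponin that was present before the procedure. The stated aim of the 5x margin, that every declared win should reflect a clinically meaningful difference, is then not met. Whoever programs the analysis would also have to choose a reading for a primary-endpoint tier.

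**Working it through.** **When a reversal occurs.** Let b be baseline and p peak, in multiples of URL, with increase = p − b. Let A have the higher peak, so that B wins on peak.

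Increase(B) − increase(A) = (bA − bB) − (pA − pB).

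The pair is not a tie, and B wins with the larger increase, exactly when bA − bB > 5 + (pA − pB). Since pA > pB, this needs bA > 5. A's MI then requires an increase above 5, so B's increase is above 10. If both baselines are at or below URL, the baseline gap is below 1 and no reversal is possible.

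**Worked pairs.** All patients meet the section 7.4 definition, with raised baselines taken as stable or falling: p > 5 if b ≤ 1, otherwise p > max(b + 5, 1.2b).

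| Pair (x URL) | Increases | Peak gap | Step 5 as written |
|---|---|---|---|
| A 6→11.2 (threshold 11); B 0.5→11.0 | 5.2; 10.5 (differ by 5.3) | 0.2 | B wins with twice the increase |
| A 50→62 (threshold 60); B 0.5→40 | 12; 39.5 (differ by 27.5) | 22 | B wins with over three times the increase |
| A 10→30; B 0.5→30 | 20; 29.5 (differ by 9.5) | 0 | Not a tie, but no winner defined |
| A 60→75 (threshold 72); B 0.5→14 | 15; 13.5 (differ by 1.5) | 61 | Tie |

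The readings also diverge from one another. Take A 20→30 (increase 10) and B 0.5→25 (increase 24.5). As written, B wins. With increase for both clauses, A wins (14.5 > 5). With peak for both, it is a tie (gap exactly 5). Under the rationale sentence's boundary of at least 5x, that same gap would count as a win.

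**How often.** The protocol gives no troponin distribution, so every input in this list is an assumption:
- 15, 30, 50 or 60% of patients have a raised baseline, with median 5, 10 or 20x URL (lognormal, log-SD 1.0, floored at URL); the others are uniform on 0.05 to 1x.
- The rise is lognormal with median 3x and log-SD 1.0 or 1.5, and peak = baseline + rise.
- For the win ratio, the rise in the intervention arm is multiplied by 0.7.

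This gives 4 × 3 × 2 = 24 settings. The one constraint taken from the protocol is section 10.2, which plans on a 50% control rate at 12 months for the whole composite. The periprocedural MI rate alone should not exceed that. These settings give 28–39%. Results:
- Reversals: 0% with no raised baselines; otherwise about 0.2–1.8% of all Step 5 wins.
- Step 5 win ratio: lower as written than with increase for both, by about 0.001–0.010.

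**Carried to the overall Win Ratio.** Assume that Step 5 settles 40% of decided pairs and that Steps 1–4 have a win ratio of 1.43. A win ratio W is a win share of W/(1 + W), so 1.43 gives 0.5885. In my run the largest Step 5 shift was from about 1.77 to 1.78, that is, shares of 0.6390 and 0.6403.
- As written: 0.6 × 0.5885 + 0.4 × 0.6390 = 0.6087, giving 0.6087/0.3913 = 1.556.
- Increase for both: 0.6 × 0.5885 + 0.4 × 0.6403 = 0.6092, giving 0.6092/0.3908 = 1.559.

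The difference is about 0.003.

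**The case against.** The strongest reply is that increase is loose wording for level. The rationale sentence speaks of troponin level, and on that reading one measure governs and nothing reverses. This may be what was meant. But the sentence names neither peak nor increase, and its boundary differs from Step 5's, so it cannot decide between them. Adopting that reading still requires a change to Step 5.

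A second reply is that the analysis plan will settle it. That would answer an omission. Here the protocol fixes the rule itself, and fixes it inconsistently.

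A third reply is that the effect is small, and this stands. Section 10.2.1 itself expects longer follow-up to leave more comparisons "determined by components higher-up the hierarchy than peri-procedural MI".

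Three stronger readings are tempting and are not supported:
- *That the effect is sizeable.* With larger assumed rises (median 10x or 20x), reversals reach about 9% of Step 5 wins and the Step 5 win ratio shifts by up to 0.064. But a mid-range setting of that kind (30% raised, medians 10x and 10x) implies periprocedural MI in about 77% of control patients, and the most extreme (60% raised, medians 20x and 20x) about 88%. Neither fits a planned composite rate of 50%.
- *That the rule biases the comparison.* Baselines are balanced in expectation by 1:1 randomisation, so reversals add noise and do not favour an arm.
- *That the simulation shows increase to be the better measure.* It applies the treatment effect to the rise and treats baseline as independent noise, so increase is bound to come out ahead.

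**Conclusion.** The inconsistency is real and follows from the text by arithmetic. Read literally, Step 5 can award a both-MI pair to the patient with the larger rise, can leave a pair with no defined winner, and can tie patients whose peaks are far apart. Nothing elsewhere in the protocol reconciles the two measures.

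Its importance is minor. It needs a raised baseline, affects only the last tier, and concerns only pairs in which both patients have a periprocedural MI. Under distributions compatible with the 50% planning rate, roughly 0.2–2% of Step 5 wins reverse, the Step 5 win ratio moves by about 0.01 or less, and the overall Win Ratio by less than about 0.004. As a rough yardstick, 150 events give a log hazard ratio standard error of 2/√150 = 0.163, and a change from 1.556 to 1.559 is about 0.002 on the log scale.

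These sizes rest on assumed distributions and on a planning rate, not on observed data. The simulation leaves out rising baselines. The finding itself, that the rule is inconsistent, rests on none of these assumptions.

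**What to change.** Before database lock and unblinding, amend Step 5 so that one measure governs both the winner and the tie, and align the rationale sentence with it: same measure, win only if the difference exceeds 5x URL, and limited to both-MI pairs. The comparison of MI with no MI stays as it is.

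Either measure removes the conflict:
- **Increase for both.** This fits the baseline-relative MI definition in section 7.4 and keeps the existing tie clause. The smaller increase wins if the increases differ by more than 5x URL; otherwise the pair is tied. State the reference value as the one already used to adjudicate that patient's MI: the baseline or, where baseline was rising, the predicted value.
- **Peak for both.** This is equally consistent internally, but it changes which pairs are tied.

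The cost is a short protocol amendment and slight reprogramming. The version history shows that these criteria were already amended once, in version 1.2. Because the trial is open-label, the change should be dated and documented as made without sight of results by arm.

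No new data are needed, since baseline and peak are already recorded. The checklist in section 19.4 schedules one pre-PCI troponin within 24 hours, which alone would not give a predicted value. But any patient adjudicated under the rising-baseline rule must already have one, so it can be carried over.
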